Abbreviations and Definitions of Terms.....	4
Protocol Synopsis	5
1 BACKGROUND AND RATIONALE	9
2 STUDY OBJECTIVES.....	13
3 INVESTIGATIONAL PLAN.....	13
5 STUDY EVALUATIONS AND MEASUREMENTS.....	18
6 STATISTICAL CONSIDERATION.....	21
7 STUDY PROCEDURES	24
8 DATA COLLECTION AND MANAGEMENT	24
9 CONSENT PROCESS.....	Error! Bookmark not defined.
10 MANAGEMENT AND REPORTING OF ADVERSE EVENTS/ADVERSE REACTIONS	26
11 REFERENCES	28
16 APPENDIX	31

Abbreviations and Definitions of Terms

Abbreviation	Definition
AE	Adverse Event
CAT	COPD Assessment Test
COPD	Chronic obstructive pulmonary disease
DPI	Dry Powdered Inhaler
FEV1	Forced expiratory volume in 1 second
FVC	Forced vital capacity
MDI	Metered dose Inhaler
mMRC	modified Medical Research Council
mBorg	modified Borg dyspnea scale
PIFR	Peak inspiratory flow rate
PRO	Patient reported outcome
RV	Residual Volume
sPIFR	Suboptimal peak inspiratory flow rate

Protocol Synopsis

Study Title	Peak Inspiratory Flow Rate in COPD Patients
Study Rationale	Recent studies have reported that some COPD patients may have a suboptimal ability to generate a sufficient inspiratory effort to achieve adequate lung delivery of inhaled medications through dry powder inhalers. Sparse data is available about the inspiratory capacity of these patients in the home setting, whether clinically stable or when experiencing worsened respiratory symptoms outside the acute care setting. Thus, we are undertaking this study to better understand the proportion of patients with suboptimal peak inspiratory flow rate (sPIFR) measurements amongst COPD patients receiving dry powder inhaler(s) (DPI) in the ambulatory setting. Further, we seek to characterize PIFR over time, the variability of PIFR measurements, and the associations with potential predictors (demographics, clinical, PRO, body position, and device) as well as exacerbations frequency and change in PIFR around period of exacerbation.
Study Endpoint(s)	
Primary Endpoint For each patient, the occurrence of suboptimal Peak Inspiratory Flow Rate (sPIFR) over 24 weeks. sPIFR will be defined as any two consecutive measurements on different days below the optimal threshold for any prescribed DPI (e.g., <30 L/min for Handihaler® (High resistance DPI), <60 L/min for Ellipta® (Medium resistance DPI))
 
Exploratory Endpoints
 
 • PIFR Endpoints 
 ▪ Time to first occurrence of sPIFR (in days) ▪ Number and proportion of sPIFR ▪ Rate of sPIFR, defined as the number of sPIFR / number of days in the study, multiplied by 30 as sPIFR/month. • Exacerbation Endpoints Occurrence (yes/no), number, severity (mild, moderate, severe) and rate of COPD exacerbations over 24 weeks. Mild, moderate and severe exacerbations will be defined as: 
 ▪ Mild – doubling use of inhaled rescue medication \geq 48 hours and not meeting definition of moderate or severe ▪ Moderate – increased rescue medication and either oral corticosteroid or antibiotics, not requiring hospitalization; ▪ Severe – hospitalization for exacerbation

Test Article(s) (If Applicable)	Measurement of PIFR using the InCheck Dial® device and quantification of respiratory symptoms and COPD exacerbations using standardized questionnaires in the patient's home setting and during research visits in the clinic setting.
Funding Source	Boehringer Ingelheim Pharmaceuticals Inc.
Study Design	Prospective, monocenter, observational study in 120 COPD patients over a 24 week period with six study visits.
Subject Population key criteria for Inclusion and Exclusion:	
Inclusion Criteria:
 
 • Age > 50 years-old • Spirometry-confirmed diagnosis of COPD (FEV1/FVC <0.70) • GOLD II-IV based on existing spirometry results • CAT score > 10 • For high resistance DPI, baseline PIFR < 90 L/min (InCheck DIAL®) and >=30 L/min; for medium resistance DPI, PIFR ≤ 90 L/min (InCheck DIAL®) and >=60 L/min. Handihaler is a high resistance DPI. Examples of medium resistance DPI: Anoro, Incruse, Breo Ellipta®, Advair® Diskus® DP or Wixela® Inhub® • History of smoking tobacco products > 10 pack years • Prescribed at least one daily maintenance DPI with no change in prescription within the four weeks prior to the Enrollment Visit • One or more exacerbations of COPD requiring systemic corticosteroids within last 3 years • Patients will be enrolled with regards to the below pre-specified characteristics based on gender and the prescribed maintenance inhaler(s) as follows (note that patients are commonly prescribed multiple inhalers): 
 ▪ Male:Female ratio 1:1 (+ 10%) ▪ Target recruitment stratified to two treatment arms: ▪ N=60 patients receiving medium resistance DPI (Anoro, Incruse, Breo Ellipta®, Advair® Diskus® or Wixela® Inhub® DPI) with planned recruitment to include 50% of participants on Diskus®/ Inhub® and 50% on Ellipta® ▪ N= 60 patients receiving high resistance DPI (Spiriva Handihaler® DPI)

	
Study participants may also receive another MDI, Respimat® inhaler, or DPI (e.g. Breo Ellipta® + Spiriva Respimat®, Symbicort MDI® + Spiriva Handihaler®, Advair Diskus® + Spiriva Handihaler®, Wixela® Inhub® + Spiriva Handihaler®) Subjects will be placed into one of the two cohorts based on the DPI, if on more than one DPI, they will be placed into the cohort for the DPI with the highest resistance (Handihaler>Ellipta=Diskus=Inhub). These strata are for recruitment only, and PIFR measurement for both DPIs will be recorded and used in analyses.
 
Exclusion Criteria:
 
 • Inability to demonstrate proper technique for the InCheck DIAL® device • Inability to achieve minimum PIFR for prescribed DPI(s) at screening/enrollment visit (< 30 L/min for e.g., Handihaler® (High resistance DPI), < 60 L/min for Ellipta® (Medium resistance DPI)) • Neuromuscular disease associated with weakness • Any condition that, in the opinion of the site investigator, would compromise the subject's ability to participate in the study. • Pneumothorax within the past 4 weeks
Number Of Subjects	N=120
Study Duration	Each participant's duration of involvement will last 24 weeks.
Study Phases Screening Study Enrollment Follow-Up	Visit 1- Screening Visit Visit 2- Enrollment Visit Home monitoring of PIFR and PRO over 24 weeks Visits 3, 4, 5, 6: Telephone Visits
Efficacy Evaluations	Changes in PIFR and dyspnea (modified Borg) that occur in the COPD population in the home setting during periods of stable respiratory symptoms and periods of worsening will be measured and recorded by participating subjects. PIFR measurements, PRO (mMRC, modified Borg, CAT) will also be undertaken in the research clinic setting. PRO will also be completed with each telephone-based study visit. This study will not be powered to definitely test for efficacy of different inhalers.

Safety Evaluations	Minimal risk
Statistical And Analytical Plan	Primary analysis will be descriptive. The primary endpoint will be described as the proportion of patients with suboptimal PIFR and reported with 95% confidence intervals. Suboptimal PIFR will be defined as any two consecutive measurements on different days below the optimal threshold for any prescribed DPI (<30 L/min for High resistance, <60 L/min for Medium resistance). Descriptive analysis of PIFR measurements, including mean (SD), median (IQR), range over time per patient per device, and in different body positions, will be conducted. The time of first occurrence of sPIFR will be reported in days and will be plotted with a Kaplan-Meier curve. We will explore, for each device, with logistic regression (binary) or negative binomial (count) the clinical and demographic factors associated with sPIFR measurements. Correlation of PIFR with CAT score, mBORG and mMRC score will be conducted. The associations between exacerbations and PIFR will be explored in different ways, for all exacerbation, stratified by severity of exacerbations, and stratified by device. See section 6.1 to 6.3 for detailed statistical plan.
Data and Safety Monitoring Plan	Data will be managed on REDCap, developed by PI of study. The PI and study staff will review data collection forms on an ongoing basis for data completeness and accuracy as well as protocol compliance. The PI will be responsible for data quality management and ongoing assessment of safety.

1 BACKGROUND AND RATIONALE

1.1 Introduction

The optimal management of chronic obstructive pulmonary disease (COPD) is important at population and health system levels due to substantial costs, morbidity and mortality. At the individual patient level, experiencing shortness of breath, often on a daily basis, with periods of worsening symptoms, can have a big impact on quality of life, productivity, and outcomes. Inhaled medications are the most effective therapies for symptom relief and available for COPD patients—particularly when given in combination. (GOLD 2017) Inhaled therapies are available as metered dose inhalers (MDI), soft-mist inhalers (SMI), dry powder inhalers (DPI), and by nebulization. Although DPI's are breath-actuated and tend to be easier for patients to use than the MDI or SMI, there is emerging evidence that delivery from DPI and drug stability of the powder is suboptimal in some patients and settings. It has recently been shown that COPD patients can exhibit suboptimal inspiratory rates during exacerbations in the hospital ([Loh, Sharma](#)) as well as in the outpatient setting ([Sulaiman 2017a, Jansenns](#)); it is unclear what impact this may have on the efficacy and safety of DPIs. Several population-based studies from the United Kingdom report that a DPI (Diskus® inhaler), with relatively low respirable mass (portion delivered into target airways) and larger particle size is associated with greater COPD exacerbation frequency and oropharyngeal side-effects compared to inhalers with a higher respirable mass in both COPD and asthma patients. ([Price, Jones, Dekhuijzen](#)) Although published evidence regarding suboptimal delivery from DPIs in the COPD population is emerging, substantial knowledge gaps exist, including peak inspiratory flow in ambulatory COPD patients when clinically stable and during periods of worsened respiratory symptoms. This specific knowledge gap is the principal basis of our investigation.

1.2 Name and Description of Procedures

This is an observational study but certain study procedures and PROs will be measured in the study. The proposed procedure is measurement of peak inspiratory flow rate (PIFR), using a device called In-Check DIAL® (Alliance Tech, Granbury, TX), and recording of respiratory symptoms in COPD patients in the home setting. This device has been used in the clinical and research settings for more than a decade.

1.3 Relevant Literature and Data

Factors that can influence optimal delivery of inhaled drug therapy in the obstructive lung disease population include the inhalational device as well as the drug and formulation and patient characteristics such as cognition, disease severity, and clinical status of the patient. Important device characteristics include overall ease of use, aerosol particle size, fine particle fraction or dose, and in the case of DPIs, the inspiratory resistance inherent to the inhaler. Of the three types of multi-dose inhalers, the MDI is the most difficult device to use correctly, particularly in the elderly COPD patient, whereas DPI breath-activated devices tend to be easier to use. The fine particle fraction, the portion of the emitted dose in the respirable range of 1-5 microns that is most likely to reach target airways, varies widely among different multi-dose inhalers: 12-35% for DPIs, 10-50% for MDI, and ~ 30% for SMI. It has been shown that a higher fine particle fraction can result in greater lung delivery into the peripheral airways (Pitcairn) - COPD is a disease that also affects the small airways. For the SMI and MDI, a slow, deep inspiration delivers the most respirable particles, whereas for the DPI, a rapid deep breath is required to de-agglomerate the powder. As noted previously, some COPD patients are not able to generate an adequate inspiratory effort with the DPI in order to achieve adequate lung drug delivery.

Depending on the DPI, the minimum peak inspiratory flow rate (PIFR) ranges from 30 L/min for the Handihaler® to 60 L/min for the Diskus® and Ellipta® DPI's. ([name] 2017, Mahler 2017). The Handihaler® is a high-resistance DPI, whereas the Ellipta® and Diskus® are classified as medium-resistance inhalers. In vitro studies indicate that the fine particle dose from Diskus®, and Ellipta® DPIs can be reduced when inspiratory flow rate decreases below 60 L/min (Buttini, Feddah, Yokohama, Grant, Prime), whereas other studies showed little effect. (Hamilton) Recent studies in humans are finding that inhaled drug delivery with the Diskus® is suboptimal when the PIFR decreases below 60 L/min. In a study of healthy volunteers using the Diskus® inhaler, a decrease in the PIFR from 60 to 30 L/min resulted in 30% decrease in blood levels of albuterol and fluticasone ([Sulaiman 2017b](#)), indicative of decreased lung delivery. (Lipworth) A recent study evaluated errors made by COPD patients using the Diskus® over a one month period in the ambulatory setting post-hospitalization. For this study, an audio monitoring device (INCA) was attached to the inhaler to measure the inspiratory flow rate and monitor adherence. Subjects were educated on the proper use of the inhaler prior to discharge from the hospital. The most frequent error made by patients was an inadequate inspiratory effort in nearly one-half of the COPD patients. ([Sulaiman 2017b](#)) It is possible that PIFR may have been lower as a consequence of the recent exacerbation. In a study conducted in an outpatient research setting, using an instrumented Ellipta® inhaler, it was found that severe to very severe COPD patients had shorter inspiratory times and tended to have impaired inspiratory flow (< 60 L/min) through the device. (Prime) It appears that lung

delivery with the Diskus® and Ellipta® may be suboptimal between 30 L/min and 60 L/min. The aforementioned data is the basis for the use of target PIFR values for Handihaler®, Diskus®, and Ellipta® devices (30 L/min, 60L/min, and 60 L/min, respectively) for the current study. We have also chosen to only enroll patients with a PIFR \leq 90 L/min at a medium resistance PIFR setting (Ellipta®) in order to select a cohort that has a reasonable probability that their PIFR may approach the minimally acceptable value for their prescribed DPI(s) with worsened symptoms.

Patient-related impediments to achieving this minimum inspiratory flow in the COPD population include age, gender, and stature (Seheult, [Mahler 2013](#)). Mahler reported that persons most likely to have an impaired PIFR are the elderly and females, (Mahler 2013), thus the rationale for having an equivalent number of males and females participate in the present study. Another factor that could affect inspiratory flow in the COPD patient is the physical position of the patient when using their DPI (standing, sitting, supine). It has been shown that peak expiratory flow rate (Wade) and other pulmonary function test measures (Wallace) including forced residual capacity are lower in a supine position than in a standing position. Therefore it is possible that a hospitalized COPD patient in a supine position, particularly with worsened respiratory status, could have decreased lung deposition from a DPI because of impaired inspiratory ability. Another scenario that a COPD patient could have impaired inspiratory capability is a morbidly obese subject using their DPI in a sitting position, where the diaphragm is displaced upwards and thus the lungs are less capable to generate a strong inspiratory effort. To our knowledge, the effect of physical position of the COPD patient on PIFR has not been investigated.

Disease related factors that could affect a patient's inspiratory ability include diaphragmatic dysfunction, air trapping, narrowing of the airways, and worsening respiratory symptoms such as during an exacerbation. (Broeder, Jansenns, Malmberg, Taube, Loh, Sharma). In COPD patients with air trapping, it was shown that in addition to a reduced forced residual capacity and decreased inspiratory capacity, the inspiratory flow was also reduced. (Taube) Decreased inspiratory flow has been shown when COPD patients are clinically stable ([name], Janssen, Mahler, Seheult) and during exacerbations requiring hospitalization. (Broeder, Loh, Sharma) Studies by Loh and Sharma found that impaired PIFR, below minimums for DPIs, occurred in a third or more of COPD patients with acute exacerbations requiring hospitalization. The study by Loh indicated patients with impaired PIFR were at a greater risk of all cause 90-day re-hospitalization, whereas this was not found in the study by Sharma. In the study by Loh, the PIFR was performed in patients while in a sitting position. (personal communication) The decrease in inspiratory flow and capacity apparently persists for some time after exacerbations. Broeder reported that PIFR, using the InCheck DIAL®, increased between 17% and 22% between hospital admission and 5 weeks later when patients were clinically stable in the outpatient setting. There are no published studies that

have measured longitudinal changes in PIFR in ambulatory COPD patients when clinically stable and during periods of worsened respiratory symptoms and recovery.

The In-Check DIAL® has been used for both clinical and research purposes for over 15 years to mimic the resistance to inspiration through DPIs. The In-Check G16 DIAL® (Alliance Tech Medical, Granbury TX) is a simple hand-held device that measures PIFR via a brief inspiratory maneuver. Measurement consists of a simple, 1-2 second inhalation requiring less user effort than an incentive spirometer. The best of three efforts are recorded. The InCheck DIAL® is designed to simulate the internal resistance of different inhalers and measure the PIFR against a specific level of resistance, either to assess a patient's ability to achieve a minimum effort recommended for DPI or to train patients on the proper inspiratory effort needed for a specific inhaler. The InCheck DIAL® measures PIFR between 15 and 120 L/min with a +/- 10% accuracy and has a repeatability of 5 L/min. Calibration of the device was shown to meet American Thoracic Society (ATS) standards through testing with an ATS waveform generator. The device includes a one-way disposable mouthpiece, measurement diaphragm, and a directly visualized PIFR scale. Importantly, the device also includes an adaptor with adjustable resistances to mimic nine resistance groups encompassing the popular MDIs and DPIs currently commercially available. These have been used repeatedly for both research and clinical purposes since 1991 (Broeder). Using these measurements against a set resistance, one can assess the frequency and degree of suboptimal PIFR in COPD patients with moderate to very severe obstruction in the home setting.

To inform this application, [name] and [name] have previously obtained IRB approval for a study to measure PIFR using the In-Check DIAL® in a clinic-based, stable COPD patient population prescribed maintenance inhalers and free of recent exacerbation, as well as a group of healthy controls (UNC IRB 16-3343; PI [name]; data presented by [name] et al ATS 2017). Over a four month period, 27 COPD patients and 19 healthy controls were recruited ([name] 2018). Among COPD patients, 20/27 (74%) were able to generate PIFR >120 L/min when no internal resistance was applied. However, PIFR (mean \pm SD) was 61 ± 13 L/min with Diskus® resistance and 36 ± 10 L/min with Handihaler® resistance. In the COPD patients, 11 used a medium resistance DPI alone, 25 a high resistance DPI alone, and 14 were receiving both a medium and high-resistance DPI.

Among the healthy controls, 19/19 (100%) were able to generate PIFR >120 L/min when no internal resistance was applied. PIFR was 97 ± 13 L/min with Diskus® resistance and 55 ± 7 L/min with Handihaler® resistance. Overall, 15 (55%) of COPD patients were not able to generate optimal PIFR (defined as >45L/min for this study) on at least one prescribed DPI. Compared to COPD patients able to generate optimal PIFR, discordant COPD participants had a greater prevalence of uncontrolled COPD (defined as COPD Assessment Test \geq 10): 93% versus 83%. Among nine

participants with repeated measures over two weeks, there were no statistical differences between intersession measurements for any inhaler resistance setting. These preliminary data demonstrate that suboptimal PIFR is common in stable COPD and may correlate with symptom burden.

Preliminary data has also demonstrated stability in PIFR over 2-4 weeks, suggesting this is inadequate duration to capture full spectrum of variability. Specifically, preliminary data from 15 COPD participants who underwent repeated measures at two to four weeks showed that participants using low-medium resistance inhalers did not have a difference in PIFR measurements at baseline versus follow-up (65 L/min on visit 1 and 64 L/min on visit 2; $p=0.69$). Of the 14 participants on a high resistance inhaler, there was no difference in baseline and repeated PIFR measurement (38 L/min on visit 1 and 38 L/min on visit 2; $p=0.46$). A study duration of 24 weeks has been selected to ensure adequate duration to capture normal variability of PIFR as well as need for adequate duration to capture COPD exacerbation events (an important exploratory outcome).

2 STUDY OBJECTIVES

2.1 Objectives:

- The primary objective of the study is to determine the proportion of patients with suboptimal peak inspiratory flow rate (sPIFR) measurements amongst COPD patients receiving dry powder inhaler(s) (DPI) in the ambulatory setting.
- The exploratory objectives are to characterize PIFR over time, the variability of PIFR measurements, and the associations with potential predictors (demographics, clinical, PRO, body position, device)
- Additionally, we will explore the exacerbations frequency and change in PIFR around period of exacerbation.

3 INVESTIGATIONAL PLAN

3.1 Study Design

This prospective, monocenter, observational study will be conducted over 24 weeks. The **Study Procedures and Assessments** (Appendix 1) are shown in the table and are also described further

3.2 Allocation to Treatment Groups and Blinding

All enrolled subjects will undergo the same procedures. There will be no blinding of subjects or study personnel to any aspect of the study.

3.3 Study Duration, Enrollment and Number of Subjects

Study duration and timeline: The duration of study is 24 weeks.

Enrollment: Participants will be recruited from UNC Clinics.

Number of subjects: One hundred twenty patients will be enrolled into this study.

Enrollment to ensure balance of seasonal effects across all arms: Enrollment such that the 24 week study period for each subject includes >2 months during the 'exacerbation season' of October – March (this translates into April and May being the only months to not enroll patients). Screening visits can be undertaken during these two months (April and May).

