3.4 Study Population

Our study population will be outpatients with moderate, severe, or very severe COPD.

Participants will be recruited from multiple sources as described above.

Inclusion Criteria:

- Age > 50 years-old
- Spirometry-confirmed diagnosis of COPD (FEV1/FVC <0.70)
- GOLD II-IV based on existing spirometry results
- CAT score > 10
- For high resistance DPI, baseline PIFR < 90 L/min (InCheck DIAL®) and >=30 L/min; for medium resistance DPI, PIFR ≤ 90 L/min (InCheck DIAL®) and >=60 L/min. Handihaler is a high resistance DPI. Examples of medium resistance DPI: Anoro, Incruse, Breo Ellipta®, Advair® Diskus®, or Wixela® Inhub® DPI
- History of smoking tobacco products > 10 pack years
- Prescribed at least one daily maintenance DPI with no change in prescription within the four weeks prior to the Enrollment Visit
- One or more exacerbations of COPD requiring systemic corticosteroids within last 3 years
- Patients will be enrolled with regards to the below pre-specified characteristics based on gender and the prescribed maintenance inhaler(s) as follows (note that patients are commonly prescribed multiple inhalers):
 - Male : Female ratio 1:1 (+ 10%)
 - Target recruitment stratified to two treatment arms:

- N=60 patients receiving medium resistance DPI (Anoro, Incruse, Breo Ellipta®, Advair® Diskus®, or Wixela® Inhub® DPI) with planned recruitment to include 50% of participants on Diskus® and 50% on Ellipta®
- N= 60 patients receiving high resistance DPI (Spiriva Handihaler® DPI)

For all study participants, participants may also receive another MDI, Respimat® inhaler, or DPI (e.g. Breo Ellipta® + Spiriva Respimat®, Symbicort MDI® + Spiriva Handihaler®, Advair Diskus® + Spiriva Handihaler®, Wixela® Inhub® + Spiriva Handihaler®) Subjects will be placed into one of the two cohorts based on the DPI, if on more than one DPI, they will be placed into the cohort for the DPI with the highest resistance (Handihaler>Ellipta=Diskus=Inhub). These strata are for recruitment only, and PIFR measurement for both DPIs will be recorded and used in analyses.

Exclusion Criteria:

- Inability to demonstrate proper technique for the InCheck DIAL® device
- Inability to achieve minimum PIFR for prescribed DPI(s) at screening/enrollment visit (< 30 L/min for e.g., Handihaler® (High resistance DPI), < 60 L/min for Ellipta® (Medium resistance DPI))
- Neuromuscular disease associated with weakness

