4.2 Study Visits

There will be six study visits/encounters over a 22-26 week period as shown in the Study Procedures and Assessments Table. Two study visits will occur at the UNC Clinics (Visits 1 and 2)

and four visits will only involve a telephone interview of subjects by study personnel (Visits 3, 4, 5, and 6).

Visit 1- Screening Visit

At Visit 1, after obtaining written informed consent, a clinical history will be obtained from the patient and if the subject meets all inclusion and exclusion criteria, a CAT score will be determined. The patient will undergo PIFR assessment based on prescribed DPI. PIFR will be recorded with best approximation to nearest 1 L/min. Subjects will be excluded if PIFR > 90 L/min based on Ellipta® and Diskus® setting or inability to achieve minimum PIFR for prescribed DPI setting (< 30 L/min for Handihaler®, < 60 L/min for Ellipta®, Diskus®, or Inhub®). The PIFR will be performed in triplicate by the patient at the recommended device setting (based on patient's DPI specific internal resistance) in the physical position (e.g. sitting) that the patient normally uses to self-administer their inhaler(s). Further, they will be instructed to perform the PIFR consistent based on the manufacturer instructions for proper DPI inhalation technique (e.g. Ellipta®, Diskus® DPI, , Inhub®) "Breathe out gently and breathe in steadily and deep"). For the Handihaler®, subjects will be instructed as follows – "Breathe out completely in one breath. Empty your lungs of air. Breathe in deeply until your lungs are full." If the patient meets the inclusion and exclusion criteria including a PIFR < 90 L/min, they can proceed to Visit 2 (Enrollment) either during the same encounter or scheduled within 30 days. If there is greater than 30 days between Visit 1 and 2, another informed consent will be reviewed and signed.

For inclusion, historical spirometry is required to be documented to ensure patients meet the GOLD definition of COPD using airflow obstruction. Most recent spirometry data will be used for characterization of the enrolled cohort. No spirometry testing will be performed as part of this study.

Visit 2- Enrollment Visit

- A physical examination including measurement of waist circumference (measured in inches horizontally through the narrowest part of the torso, between the lowest rib and the iliac crest)
- Medical history (includes exacerbations history)
- COPD medication use (maintenance and reliever)

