- We will use mixed models to explore associations of monthly PIFR averages over time and clinical and demographic factors. Subjects will be considered as random factor, other variables will be considered fixed effects.
- Association of PIFR with CAT score, mBORG score and mMRC
 - Association of PIFR and CAT scores at V1, V3, V4, V5, V6 (for PIFR, use the measurement in the week of each telephone follow-up, or the month average)

- Correlation of change in CAT scores with change in PIFR from baseline after 24 weeks
- Association of PIFR and mBORG score at V2, V3, V4, V5, V6
- Association of PIFR and mMRC scores at V1, V3, V4, V5, V6 (for PIFR, use the measurement in the week of each telephone follow-up, or the month average)

For COPD exacerbation analyses, the proportion of patients with COPD exacerbations (from Kaplan Meier curve) and the rate of exacerbations occurring during follow-up will be reported along with 95% CI. A patient will be considered censored for exacerbations at the time of the last documented visit, the end of the study, the switching of device (between medium and high resistance DPI) or death (whichever occurs earlier), if they did not experience an exacerbation before. The exacerbations will be reported overall and stratified by severity. The associations between exacerbations and PIFR will be explored in different ways, for all exacerbation, stratified by severity of exacerbations, and stratified by device.

- The rate of exacerbations and sPIFR will be analyzed with negative binomial models (or another model if more appropriate).
- For patients with exacerbations, the mean of PIFR in the week before, of, and after each exacerbation will be calculated and reported.

All tests with p value < 0.05 will be interpreted nominally as statistically significant.

Missing data

- No imputation for PIFR
- No imputation for COPD exacerbations
- No imputation for CAT, mBORG and mMRC

Sample Size and Power

In this application, we propose to recruit 120 COPD participants for study enrollment. There are several rationales for this sample size selection.

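### Section 3.3 promises seasonal balance across arms, but its rule is only a minimum for each subject, and no analysis in 6.3 takes season into account

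*Combined protocol and SAP*

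**What the plan says.** Section 3.3 announces its enrolment rule with a purpose: "Enrollment to ensure balance of seasonal effects across all arms: Enrollment such that the 24 week study period for each subject includes >2 months". The rule in full is that the "24 week study period for each subject includes >2 months during the 'exacerbation season' of October – March". It is then put into practice as a calendar restriction: "this translates into April and May being the only months to not enroll patients".

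Section 3.4 sets targets for the size of the two device cohorts (60 and 60), the split among medium-resistance devices and the overall sex ratio. It sets none for when each cohort is enrolled.

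Section 6.3 plans a device-type subgroup of the primary endpoint and a Cox model for time to first suboptimal PIFR. It also plans a mixed model for monthly PIFR averages over time, negative binomial models for exacerbation and suboptimal-PIFR rates, and exacerbation–PIFR associations "stratified by severity of exacerbations, and stratified by device". Where covariates are described, they are demographic and clinical factors. Season, calendar month and entry date are not named. An optional descriptive summary by week or month is mentioned, but it is not tied to the calendar.

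**The concern.** Balance across arms is a property of how entry dates are distributed between the cohorts. A minimum that every subject must meet does not create it: both cohorts can comply fully and still be followed at quite different times of year.

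The protocol itself treats October to March as the period of higher exacerbation risk. If season also affects PIFR, three planned exploratory results are exposed: the medium- versus high-resistance subgroup, the association between exacerbations and PIFR, and the time effect in the mixed model. A reader who trusts the wording of 3.3 would assume that the design had dealt with this, and the analysis plan holds nothing in reserve.

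**Working it through.** **Inputs.** Follow-up is 24 weeks = 168 days (3.3: "The duration of study is 24 weeks"). The visit span of 22–26 weeks in 4.2 gives 154 and 182 days as variants. The season is October–March. Two months is read as 61 days, so more than two months means at least 62 days; this is an assumption. Non-leap years are used.

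**Formula.** For a start date d, in-season days = the number of days from d to d + 167 that fall in October–March.

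**Step 1: the plan's own translation.** In-season days by start month:

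| Start month | Days | Start month | Days |
|---|---|---|---|
| Jan | 60–90 | Jul | 76–106 |
| Feb | 32–59 | Aug | 107–137 |
| Mar | 1–31 | Sep | 138–167 |
| Apr | 0–14 | Oct | 152–168 |
| May | 15–45 | Nov | 122–151 |
| Jun | 46–75 | Dec | 91–121 |

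The translation into April and May alone does not reproduce. February and March starts fall short, and their figures are the same at 154, 168 and 182 days. Early June also falls short at 168 days. The open dates with fewer than 62 in-season days are 30–31 January (2), all of February (28), all of March (31) and 1–16 June (16). That is 2 + 28 + 31 + 16 = 77 of 365 − 61 = 304 open dates, or 25%.

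**Step 2: the range each statement allows.**
- More than two months, applied literally: starts from 17 June to 29 January, 304 − 77 = 227 dates. A 29 January start gives 3 + 28 + 31 = 62 days. A 17 June start runs to 1 December and gives 31 + 30 + 1 = 62. A start on 1–15 October gives 168. The range is 62–168 (37–100% of follow-up), with mean 118 under uniform entry. Reading two months as 59–62 days moves the lower bound to 60–63.
- Only April and May closed: a 31 March start gives 1 day. The range is 1–168, mean 97.

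**Step 3: season against study time, with entry uniform over eligible dates.** Share of person-days in October–March:

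| Rule | Week 1 | Week 12 | Week 16 | Week 24 |
|---|---|---|---|---|
| More than two months | 55% | 80% | 79% | 55% |
| April and May closed | 60% | 60% | 60% | 46% |

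Study time and season are therefore linked without any uneven accrual. Under the first rule the pattern is a symmetric hump, so it bears on month-by-month means and curvature more than on a straight-line slope. Under the second it is a late decline.

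**Step 4: can a season term be estimated?** Of the 227 compliant start dates, 106 begin in season and end outside it, 106 do the reverse, and 15 stay in season throughout. With entry spread over the year, season and time on study can be separated once season is in the model.

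**The case against.** The strongest reply is that little depends on this. The primary result is one pooled descriptive proportion. The cohorts exist for recruitment, and the synopsis says the study is not powered to test inhalers against each other. The other models are exploratory with nominal p-values, their covariate lists are open, and entry dates are held, so season could be added later. One centre recruits both cohorts from the same clinics. At the pilot's pace of 27 COPD patients in four months, 120 would take 120/27 × 4, or about 18 months, so each cohort would probably span several seasons. All of this stands, and it limits the consequence. It does not make the statement in 3.3 true, and a season term added after the data are seen is weaker than one specified now.

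Three stronger readings are tempting but not supported.
- A reader might infer that device results are bound to be confounded. That needs the cohorts to accrue at different times of year, which the documents neither predict nor prevent.
- A reader might infer that exacerbation rates by device are biased. In 6.3, exacerbations are reported overall and by severity. Device is a stratum for the exacerbation–PIFR association, so unequal timing between cohorts does not bias a listed rate contrast. Season can still confound the association within a device.
- A reader might extend the point to sex, because the 1:1 ratio in 3.4 is overall and not within cohort. But 6.3 models demographic factors for each device, and gender is among the demographics in 5.1.1, so sex can be examined within device. No nested quota is required.

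**Conclusion.** The point holds as a mismatch between a stated design property and the rule meant to deliver it, with no fallback in the analysis. Compliant subjects may have 62–168 in-season days, or 1–168 under the calendar form of the rule, and the two forms must be reconciled. The device subgroup of suboptimal PIFR, the exacerbation–PIFR associations and the mixed-model time effect can be confounded with season. For the time effect, the link with season exists even under uniform accrual.

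The size of any resulting bias is unknown, because the documents give no seasonal effect on PIFR. The day counts rest on 168 days of follow-up and 61 days for two months; the weekly shares also assume uniform entry. The primary pooled proportion is not affected as a comparison would be, although season is part of its case mix. Comparisons within patients on two devices cover the same dates and are free of season. This is worth correcting before analysis, but it does not threaten the primary result.

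**What to change.** In 6.3:
- Add a time-varying October–March indicator to the monthly PIFR mixed model and to the Cox models.
- Add each subject's share of observed follow-up in October–March to the negative binomial models.
- Report in-season days by device cohort.

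In 3.3:
- Replace the claim of balance across arms with a statement that each subject has a minimum in-season exposure.
- Reconcile the two-month minimum with the list of closed months.

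The cost is one variable derived from dates already held, one extra term in exploratory models, and one descriptive table. No new data collection is needed.
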